Cirrhosis leads to portal hypertension and development of gastroesophageal varices, which are the most common cause for bleeding in cirrhosis and a major cause of death. The American Association for the Study of Liver Disease (AASLD) recommends screening endoscopy every 2 years to evaluate for gastroesophageal varices, and annual surveillance for those with small varices on endoscopy. Unfortunately, endoscopy is costly, requires sedation, is poorly tolerated, is subject to high inter-observer variability, and is associated with risks that include bleeding, esophageal injury and aspiration. Noninvasive methods for evaluation of gastroesophageal varices are needed. CT is noninvasive, rapid, less expensive than endoscopy, requires no sedation, provides a quantitative measure of the size of the varices, and allows for assessment of para-esophageal varices, varices in other body locations, ascites, other signs of portal hypertension, patency of liver vasculature, and detection, diagnosis and staging of hepatocellular carcinoma. Single-Energy CT (SECT) has relatively high accuracy in prospective studies for detection of any and large varices but is associated with suboptimal contrast opacification of gastroesophageal varices. Dual-Energy CT with the GE scanners with GSI Xtream (DECT) improves the contrast-to-noise ratio by 60% compared to SECT and is currently standard of care at UAB for evaluation of cirrhosis. The primary objective of this study is to determine the accuracy of DECT for detecting any varices and high-risk varices. We hypothesize that the accuracy (AUROC) of DECT will be >0.90 and >0.95 for detecting any and high-risk varices in a prospective pilot study (N=50) that uses endoscopy as the reference standard. This will be a single-center pilot observational prospective IRB-approved study. We will enroll 50 adult patients presenting to UAB Endoscopy for surveillance endoscopy to detect and grade gastroesophageal varices.

2. BACKGROUND AND RATIONALE

Cirrhosis leads to portal hypertension and development of gastroesophageal varices, which are the most common cause for bleeding in cirrhosis and a major cause of death. Bleeding varices have a 6-week mortality of 15%-25%.^{1,2} About 50% of patients with cirrhosis have varices, and 30% have large varices (>5 mm) that are high risk for bleeding.³

The American Association for the Study of Liver Disease (AASLD) recommends screening endoscopy every 2 years to evaluate for varices, and annual surveillance for those with small varices on endoscopy.⁴ Patients at a high risk of bleeding with large varices, small varices and red wale signs (an endoscopic finding), or small varices and decompensated cirrhosis proceed to treatment such as prophylactic band ligation and beta blockers.^{5,6,7} Conversely, patients with no varices or small varices (≤ 5 mm) continue surveillance efforts by endoscopy to monitor for development of large varices.^{3,7,8} Unfortunately, endoscopy is costly, requires sedation, is poorly tolerated, is subject to high inter-observer

variability, cannot detect other signs or portal hypertension or para-esophageal varices that are at risk for future bleeding events, and is associated with risks that include bleeding, esophageal injury and aspiration.⁹ Many of these factors contribute to poor patient compliance with AASLD recommendations.

Noninvasive methods for detecting, grading, and risk stratification of esophageal varices are needed. Imaging tests such as ultrasound elastography to measure liver stiffness have been proposed as a method to predict the presence of varices but have insufficient accuracy to eliminate the need for endoscopy.¹⁰ An ideal biomarker to screen for esophageal varices would be part of the routine standard of care of patients with cirrhosis, noninvasive, rapid, less expense than endoscopy, highly accurate, highly reproducible, and would require no sedation, provide a quantitative measure of the size of the varices, provide a mechanisms to assess the risk of future bleeding, allow for an assessment for other signs of portal hypertension, and provide other benefits to the patient (e.g. detect ascites and HCC and assess liver vasculature).

Computed tomography (CT) is standard of care to screen for HCC. CT is noninvasive, rapid, less expensive than endoscopy, requires no sedation, provides a quantitative measure of the size of the varices, and allows for assessment of para-esophageal varices, varices in other body locations, ascites, other signs of portal hypertension, patency of liver vasculature, and detection, diagnosis and staging of HCC. Conventional Single-Energy CT (SECT) has relatively high accuracy in prospective studies for detection of any and large varices and has higher inter-observer agreement than endoscopy (kappa 0.56 vs. 0.36, respectively).¹¹ Major deficiencies in SECT include relatively suboptimal contrast opacification of gastroesophageal varices, inconsistent accuracy that is dependent upon SECT image acquisition technique, and suboptimal stratification of the risk of bleeding (e.g. inability to detect red wale sign) compared to endoscopy.

Dual-Energy CT (DECT) improves the contrast-to-noise ratio by 60% compared to SECT. DECT also improves visualization by taking advantage of the markedly increased attenuation of iodine at photon energy levels just above the iodine K edge (33 keV). Using material decomposition techniques, DECT can map the concentration of iodine on a voxel by voxel basis which, combined with higher contrast to noise resolution on these same type of images, improves the conspicuity of enhancing structures. DECT is routinely used at the University of Alabama at Birmingham (UAB) to screen for HCC in cirrhotic patients.

While DECT has been shown to improve image quality and portal venography compared to SECT, the accuracy of DECT for screening for varices has not been reported.

3. OBJECTIVES

3.1 Primary Objective

To determine the accuracy of dual energy CT for detecting any varices and high-risk varices in patients with cirrhosis presenting for upper gastrointestinal endoscopy.

3.2 Secondary Objectives

- 3.2.1** To assess inter-observer agreement for the detection of any varices and high-risk varices on dual energy CT.
- 3.2.2** To compare the accuracy of grade of varices on CT to grade of varices on endoscopy for predicting gastroesophageal variceal bleeding at 2 years.
- 3.2.3** To develop and compare the accuracy of multivariate statistical models designed to predict 2-year risk of bleeding gastroesophageal varices, both without and with dual energy CT findings.
- 3.2.4** To predict 2-year liver-related events using the variceal grade on DECT, LSN score and MELD score.

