4. PARTICIPANT SELECTION

This will be a single-center pilot observational prospective IRB-approved study. We will enroll 50 adult patients presenting to UAB Endoscopy for surveillance endoscopy to detect and grade gastroesophageal varices and follow up with patients for at least 2 years. These patients will present to the Highlands Gastroenterology Endoscopy Center or to the Kirklin Clinic Gastroenterology Endoscopy Center and will be seen by sub-investigator [name], a hepatologist and gastroenterologist. Approximately 8 to 10 patients per week are expected to meet final inclusion criteria, and we anticipate that we will approach 100 patients about study participation to accomplish 50 recruited patients over 9 months.

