13.1 Sample size justification

[name] (co-investigator and biostatistician) will conduct and supervise all statistical analyses. This is a prospective study to determine the accuracy of dual energy CT for detecting any varices and high-risk varices in patients with cirrhosis presenting for upper gastrointestinal endoscopy. The endpoint of the primary objective is accuracy which is determined by the Area Under the Curve (AUC) using Recursive Operating Characteristics (ROC) analysis (AUROC). Based on published studies ^{1,2,3} in patients with detected gastroesophageal varices, we will observe 32%, 32%, and 36% with no, small, and large varices, respectively. In order to test the hypothesis: the accuracy (AUROC) of DECT will be >0.90 for detecting any and high-risk varices in a prospective pilot study that uses endoscopy as the reference standard, we plan to enroll 50 patients such that we will have 16/50, 16/50, and 18/50 with no, small, and large varices. This size of the study will have $>95\%$ power to detect any varices, e.g. (16+18)/50 small and large varices with $AUC >=0.90$ comparing to null hypotheses of $AUC=0.5$ (not detect any) using a one-sided z-test at a significance level of 0.05 controlled false positive rates at 1%.

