13.2 Statistical analysis plan

Patient and imaging characteristics will be summarized and compared using appropriate summary statistics, e.g. mean and standard deviation for continuous variables, frequency and percentage for categorical variables, and extensive exploratory data analysis and data visualizations will be utilized to assess diagnostics, identify outliers, and validate assumptions.

Receiver operating characteristic (ROC) analysis will be used in Aim 1 to estimate the accuracy of DECT for differentiating no varices from any varices and for differentiating no and small varices from large varices in Aim 1. Sensitivity, specificity, accuracy, and AUC along with their two-sided 95% CI will be presented separately. The grade of varices (0, 1, 2) on DECT will be correlated with the grade of varices on endoscopy (0, 1, 2) using weighted Kappa coefficient for categorical data (Aim 2.2).

The MIXED effect model will be used in Aim 2.1 to estimate the ICC for the inter-observer agreement for the detection of any varices and high-risk varices on dual energy CT. Reader experience and subject will be the two random effects in the model used for interobserver variability. The intraclass correlation coefficient (ICC) will be defined as the ratio between subject variance and the sum of variances for subject, reader experience and error term. ICC values will be characterized as very poor (0 to <0.20), poor (0.20 to <0.40), moderate (0.40 to <0.60), good (0.60 to <0.80), and very good (0.80 to 1.00).

Time to development of bleeding varices (or hepatic event) will be modeled in Aim 2.3 using Cox proportional hazards models with clustered sandwich estimators to account for within and between cluster correlations. Cause specific proportional subhazards analysis while accounting for competing risks (e.g. gastroesophageal banding) and adjusting for covariates will be utilized to assess the association between endoscopic findings and DECT findings and time to developing individual vs. any hepatic complications.

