A combination of variceal grade on DECT, LSN score and MELD score will have equal or greater accuracy for predicting 2-year liver-related events than a combination of endoscopic findings and MELD score. This analysis will be exploratory in Aim 2.4, but a trend may be evident and justify further investigation. Competing risks analysis will be used to assess the association of variceal grade on DECT, LSN score and MELD scores with development of liver-related events, with specific attention to 2-year variceal bleeding events. Cumulative Incidence Function (CIF) will be used to estimate the marginal probability of a liver-related event as a function of its cause-specific probability and overall survival probability.

All analysis will be carried out using SAS v 9.4.

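### Objective 3.2.3 compares bleeding models without and with DECT in the same 50 patients with no internal validation; if the models are nested, the apparent C-index will usually favour DECT even when it adds nothing

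*Combined protocol and SAP*

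**What the plan says.** Section 3.2, objective 3.2.3, is to "develop and compare the accuracy of multivariate statistical models designed to predict 2-year risk of bleeding gastroesophageal varices, both without and with" DECT findings. It does not list the predictors of either model.

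Section 4 defines the whole data set: "We will enroll 50 adult patients presenting to UAB Endoscopy for surveillance endoscopy to detect and grade gastroesophageal varices". The study is single-centre, and no second cohort is mentioned.

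For this aim, Section 13.2 says: "Time to development of bleeding varices (or hepatic event) will be modeled in Aim 2.3 using Cox proportional hazards models with clustered sandwich estimators". It adds a subhazards analysis, described as "accounting for competing risks (e.g. gastroesophageal banding) and adjusting for covariates will be utilized to assess the association" of endoscopic and DECT findings with time to complications. ROC analysis is named for Aim 1. For Aim 2.3 the section names no accuracy measure, no covariates, no expected number of bleeds, and no resampling, shrinkage or split sample.

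The one reference to validation in Section 13.2 concerns model assumptions: "data visualizations will be utilized to assess diagnostics, identify outliers, and validate assumptions". The exploratory label is given to the next aim only: "This analysis will be exploratory in Aim 2.4, but a trend may be evident and justify further investigation".

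**The concern.** A model judged on the patients used to fit it looks better than it is, and more so with more terms and fewer events. If the model with DECT is the base model plus DECT terms, it carries more of this optimism than its comparator. The difference in apparent accuracy is then tilted towards DECT. Sandwich standard errors and competing-risks methods do not address this.

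Few bleeds are plausible from the plan itself. Patients with prior variceal bleeding are excluded (Section 4.2), high-risk patients go on to prophylactic treatment (Section 2), and banding is treated as a competing event (Section 13.2). The list of possible DECT terms is long: Section 11.3.2 records variceal grade, other varices, HCC, ascites, vascular patency and LSN.

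At stake is the answer to objective 3.2.3. A pilot is used to decide whether to go further, and an uncorrected comparison can produce an encouraging result from noise.

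**Working it through.** **The plan's own figure.** The only statistical figure is in Section 13.1, for the primary objective: power above 95% for AUC 0.90 against 0.5, with 16 + 18 = 34 patients with varices and 16 without, one-sided 0.05. The Hanley-McNeil variance at A = 0.90 uses Q1 = 0.9/1.1 = 0.8182 and Q2 = 2(0.81)/1.9 = 0.8526:
- Variance = [0.09 + 33(0.8182 - 0.81) + 15(0.8526 - 0.81)]/(34 × 16) = 0.9995/544 = 0.00184, SE 0.0429.
- Null SE = √[51/(12 × 34 × 16)] = 0.0884.
- Power = Φ[(0.40 - 1.645 × 0.0884)/0.0429] = Φ(5.9), above 99.9%.

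The statement is reproduced, but it says nothing about objective 3.2.3, for which no figure is given.

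**Why nesting matters.** The base model is the larger model with the DECT coefficients set to zero, so the maximised partial likelihood cannot fall. When DECT adds nothing, twice the gain in log-likelihood is approximately chi-squared with k degrees of freedom. Its mean is k: 1 for DECT grade, 2 for grade + LSN. The C-index is not the quantity maximised, so it can fall. It usually rises.

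**Inputs.** From the documents: N = 50, grade mix 16/16/18 (Section 13.1), two-year follow-up. Assumed, because the documents are silent: the bleed count, the base model (endoscopic grade + MELD), the effect sizes, and the agreement of DECT with endoscopy. In every run DECT and LSN carry no information on bleeding beyond the base model. With four coefficients, 6 bleeds give 6/4 = 1.5 events per coefficient and 16 give 16/4 = 4.

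**Simulation A** (1,500 studies per level; hazard ratio 2 per endoscopic grade and 1.5 per SD of MELD; DECT grade with 25% one-level errors; LSN correlated 0.4 with MELD). At about 6, 10 and 16 bleeds:
- DECT grade added: mean apparent gain in C-index +0.026, +0.018, +0.013, positive in 70-73%.
- Grade + LSN added: +0.049, +0.034, +0.024, positive in 85%, 84%, 83%. Change in new patients: -0.022, -0.023, -0.019.

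**Simulation B** (400 data sets per setting; 80% DECT-endoscopy agreement; the same fitted models scored in 1,500 independent patients). The last column is apparent minus new-patient change.

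| 2-year risk (mean bleeds) | Terms added | Apparent gain > 0 | Mean apparent gain | Change in new patients | Optimism in the difference |
|---|---|---|---|---|---|
| 6% (4.0) | grade | 71% | +0.036 | -0.009 | 0.045 |
| 6% (4.0) | grade + LSN | 84% | +0.065 | -0.018 | 0.083 |
| 10% (6.2) | grade | 72% | +0.029 | -0.014 | 0.043 |
| 10% (6.2) | grade + LSN | 84% | +0.051 | -0.024 | 0.075 |
| 20% (11.5) | grade | 72% | +0.017 | -0.014 | 0.031 |
| 20% (11.5) | grade + LSN | 85% | +0.032 | -0.025 | 0.057 |
| 30% (16.5) | grade | 71% | +0.012 | -0.012 | 0.024 |
| 30% (16.5) | grade + LSN | 83% | +0.023 | -0.023 | 0.046 |

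The Monte Carlo error of a 71% share is √(0.71 × 0.29/400) = 2.3 percentage points. The likelihood-ratio test for the added terms gave p < 0.05 in about 7-13% of these null data sets. Two further checks of the nested case gave 65-73% and 66-70% positive for grade, and 84-89% and 81-84% for grade + LSN.

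**When the models are not nested.** If DECT grade replaces endoscopic grade, the mean apparent change was -0.030, -0.012 and -0.021 at about 5, 8 and 13 bleeds, positive in 32%, 40% and 30%. A second check gave 30-37%. With LSN added to that swap, the change was positive in 49%, 57% and 44%.

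**Effect of bootstrap optimism correction** on the mean C-index gain (share positive):
- A, grade + LSN: about 6 bleeds, +0.049 (85%) to +0.018 (48%); about 10, +0.034 (84%) to -0.001 (38%); about 16, +0.024 (83%) to -0.007 (34%). The corrected values rest on 200-250 studies with 60 resamples each.
- B, 60 data sets × 40 resamples: grade at about 6 bleeds, +0.030 (68%) to +0.017 (45%); grade + LSN at about 6, +0.065 (93%) to +0.031 (57%); grade + LSN at about 12, +0.033 (87%) to -0.001 (45%). The error on a 45% share here is √(0.45 × 0.55/60) = 6.4 points.

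Correction removes the average tilt towards DECT at about 10 bleeds or more, though the corrected mean still sits above the new-patient change of about -0.02. At about 6 bleeds a positive residue remains.

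**The case against.** **Nesting is not stated.** No predictor list exists for Aim 2.3, and the one comparison Section 13.2 spells out, for Aim 2.4, is a swap: DECT grade, LSN and MELD against endoscopic findings and MELD. This stands. A reader might infer that the plan favours DECT by construction, or that in-sample discrimination almost always rises. The documents do not support either. The result depends on an unstated model form, and even in the nested case DECT grade alone left the C-index unchanged or lower in nearly 30% of data sets.

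**LSN may not belong in objective 3.2.3.** It is named under 3.2.4 and not in the Aim 2.3 text, although it is measured on the DECT images. This stands, so the figures for DECT grade alone should be read first.

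**A positive point difference is not a claim of benefit.** The plan contains no such decision rule, and the likelihood-ratio test was seldom significant. This limits the point to the estimate. But the objective asks for a comparison of accuracy, so the estimate is what would be reported.

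**The true gain could be real.** With MELD alone as the base, adding DECT grade gained 0.07-0.08 apparent and 0.04-0.055 in new patients, so much of that gain was genuine. A reader might infer that overfitting is as large as any realistic true gain. That is not supported, because the documents give no expected gain.

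**This is a secondary objective of a pilot.** That bears on severity. It does not remove the bias, and the plan's exploratory caveat does not reach Aim 2.3.

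**Conclusion.** The concern holds in conditional form. Section 13.2 plans no internal validation for Aim 2.3. If the DECT model adds terms to the same base model, the apparent comparison will usually favour a DECT that adds nothing. Across the runs the apparent C-index rose in about 65-73% of studies with DECT grade (mean about +0.01 to +0.04) and about 81-89% with grade + LSN (mean about +0.02 to +0.065). In new patients it fell by about 0.01-0.03.

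These figures rest on an assumed 4 to 16 bleeds, an endoscopic grade + MELD base, assumed effect sizes and DECT-endoscopy agreement, and the C-index as the measure. Competing risks and loss to follow-up were not simulated. Selecting among many DECT findings was not simulated either, and would add optimism. The point concerns the estimate, not the significance test, and does not apply to a simple replacement of endoscopic grade by DECT grade. It should be fixed, but it does not touch the primary objective.

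**What to change.** In Section 13.2, Aim 2.3:

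1. Prespecify two small models, for example endoscopic grade + MELD, and the same plus DECT grade. State whether LSN counts as a DECT finding here.
2. Name one accuracy measure: the C-index or the 2-year time-dependent AUC.
3. Fit both models with penalisation when bleeds are few, and say what counts as few.
4. Report bootstrap optimism-corrected accuracy for each model and the corrected difference with its interval, repeating every modelling step in each resample.
5. Label Aim 2.3 exploratory, as Aim 2.4 already is.
6. Do not present the apparent difference as evidence of added value. State that the correction is incomplete with about 6 bleeds, and that no claim of added value will be made at that count or below.

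The cost is SAP wording, a resampling loop and a little more analysis time. Reported accuracies will be somewhat lower. No new patients or data are needed.

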4. PARTICIPANT SELECTION

This will be a single-center pilot observational prospective IRB-approved study. We will enroll 50 adult patients presenting to UAB Endoscopy for surveillance endoscopy to detect and grade gastroesophageal varices and follow up with patients for at least 2 years. These patients will present to the Highlands Gastroenterology Endoscopy Center or to the Kirklin Clinic Gastroenterology Endoscopy Center and will be seen by sub-investigator [name], a hepatologist and gastroenterologist. Approximately 8 to 10 patients per week are expected to meet final inclusion criteria, and we anticipate that we will approach 100 patients about study participation to accomplish 50 recruited patients over 9 months.

4.1 Inclusion Criteria

Adult patients with cirrhosis presenting to UAB Endoscopy for surveillance endoscopy to detect and grade gastroesophageal varices

4.2 Exclusion Criteria

- 4.2.1** Inability to provide written informed consent
- 4.2.2** History of bleeding gastroesophageal varices, variceal intervention or portosystemic shunt
- 4.2.3** Prior liver transplant
- 4.2.4** History of malignancy
- 4.2.5** Severe chronic kidney disease with estimated glomerular filtration rate (GFR) < 30 mL/min/1.73 m²
- 4.2.6** Presence of acute kidney injury
- 4.2.7** Prior iodinated contrast allergy
- 4.2.8** Patient weight >300 lbs
- 4.2.9** Multiphasic liver CT within 3 months of upper endoscopy
- 4.2.10** Pregnancy

4.3 Inclusion of all races and ethnic groups are eligible for this trial. There is no bias towards age or race in this trial. The trial is open the accrual of women and men.

5. RECRUITMENT AND SCREENING

5.1 Recruitment Process

Patients presenting to the Highlands Gastroenterology Endoscopy Center or to the Kirklin Clinic Gastroenterology Endoscopy Center will initially be approached by the hepatologist ([name], sub-investigator who routinely performs surveillance endoscopy procedures) to ask if the patient would be interested in the study. If the patient is interested, the study coordinator will meet with the patient prior to endoscopy, answer questions, review the inclusion/exclusion criteria, and obtain informed consent. The study coordinator will review the labs, order any missing research study labs, and schedule the DECT exam. The patients will be directed to our outpatient facilities at Leeds or

Gardendale, as both centers have a *Dual Energy GE Revolution CT with GSI Xtream* (DECT). After imaging, the patient will be given a \$75 incentive for their time, and the patient will be discharged. Patients will provide consent for a follow up interview to evaluate for liver-related events, particularly bleeding varices. The study coordinator will arrange the interview and record all data in a secure web-based REDCap research database.

